- Inquire if the participant has had a suspected or confirmed exposure to SARS-CoV-2 or developed COVID-19 symptoms in the period of Screening visit to Day 1.
- Perform rapid SARS-CoV-2 IgM/IgG antibody test.
- If WOCBP, perform urine pregnancy test (UPT).
- If WOCBP, confirm use of contraceptives.
- Alcohol breath test
- Confirm eligibility.
- Collect serum sample for SARS-CoV-2 antibody PK assessment.
- Collect NP swab sample for SARS-CoV-2 RT-PCR test.
- Targeted physical exam, if clinically indicated.
- Assess for any COVID-19 symptoms or SARS-CoV-2 exposure.
- Monitor/assess AEs related to study procedures.

Dosing – Day 1: in-clinic overnight visit.

- Collect pre-dose serum sample (within 2 hours prior to dosing) for SARS-CoV-2 antibody PK assessment.
- Vital signs (resting ≥ 10 minutes) [body temperature, blood pressure (seated), pulse, SpO₂ (pulse oximetry) and respiratory rate]; within 2 hours prior to dosing.
- Randomize.
- Administer randomized study treatment.
- Monitor/assess AEs before, during injection and post-administration in the clinic overnight.
- Vital signs (resting ≥ 10 minutes) [body temperature, blood pressure (seated), pulse, SpO₂ (pulse oximetry) and respiratory rate] at 30 minutes (± 5 mins) and 1 hour (± 10 mins) post-administration.
- Serum samples for post-dosing assessment of SARS-CoV-2 antibodies for PK at 1 hr ± 10 min, 2 hrs ± 15 min, 4 hrs ± 15 min, 8 hrs ± 30 min, and 12 hrs ± 30 min (from end of infusion/injection).
- Targeted physical exam, if clinically indicated.

Anti-SARS-CoV-2 Immunoglobulin Intravenous (Human) (NP-028), abbreviated as COVID-HIG
EBS-CVH-006, Version 3.0, 18 Feb 2022

- Record any concomitant medications (if applicable).

Post-Dosing Assessments (Days 2-57)*:

Day 2 (1±0.5 days) – in-clinic discharge visit

Day 3 (2±0.5 days), Day 4 (3±0.5 days), Day 6 (5±0.5 days), Day 8 (7±1 day), Day 15 (14±2 days), Day 29 (28±2 days), Day 43 (42±3 days): – visit can be conducted in-clinic or as home healthcare/telemedicine follow-up.

If randomized to IV group (Arm 3), omit visits on Day 3 and Day 6.

* Visits are indicated as calendar days, while the time post-dosing and the visit windows are indicated in the brackets.

Perform the following in-clinic or via telemedicine follow-up:

- Assessment of AEs and concomitant medications.

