1.5.2 Natural History of COVID-19

The incubation period for SARS-CoV-2 is approximately four to five days (range: two to seven days) (46, 47), and most individuals who develop symptoms (~98%) will do so within 11.5 days post-infection (46). Acute manifestations of COVID-19 include the following signs and symptoms: fever, cough, shortness of breath, fatigue, myalgia, nausea/vomiting or diarrhea, headache, rhinorrhea, anosmia, and ageusia. (48).

Many COVID-19 patients present with mild disease (approximately 80%). Although mild, symptomatic COVID-19 often resolves five to seven days (and up to 14 days) after symptom onset, there is growing recognition of the occurrence of postinfectious sequelae lasting for months in individuals, including young, physically fit individuals who initially experienced mild acute illness (49). Fatigue, dyspnea, cough, arthralgia, and chest pain are among the most commonly reported. Based on current available evidence, postinfectious sequelae may also include serious outcomes: cardiac (myocardial inflammation, ventricular dysfunction), respiratory (pulmonary function abnormalities), renal (acute kidney injury), dermatologic (rash, alopecia), neurologic (altered cognition, memory impairment, olfactory and gustatory dysfunction, sleep dysregulation), and psychiatric (depression and changes in mood).

Approximately 20% of patients will progress to more severe COVID-19 characterized by worsening dyspnea and hypoxia, severe pneumonia with >50% lung involvement on imaging. The median time from symptom onset to hospitalization is seven days; range: three to nine days post-symptom onset (50). Five percent of patients progress to critical COVID-19 manifested as acute respiratory distress syndrome, septic shock and/or multiorgan system dysfunction (47, 51, 52, 53). Cardiac, neurologic, hepatic, renal and hematologic complications may occur (54). Mortality in hospitalized COVID-19 patients ranges from 15% to 40% (55).

Reports of reinfection and vaccine breakthrough infections have become more frequent with emerging novel variants, but still remain relatively infrequent, with vaccination post-infection yielding a greater than two-fold reduction in reinfection risk (56).

Anti-SARS-CoV-2 Immunoglobulin Intravenous (Human) (NP-028), abbreviated as COVID-HIG
EBS-CVH-006, Version 3.0, 18 Feb 2022

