6.6 Scheduled Study Visits

Day 2, 3, 4, 6, 8, 15, 29, 43

Visits are conducted as in-clinic or telemedicine/home healthcare follow-ups.

Visit windows are as follows (in relation to Day 1):

Day 2: (1 ± 0.5 days), Day 3: (2 ± 0.5 days), Day 4: (3 ± 0.5 days), Day 6: (5 ± 0.5 days), Day 8: (7 ± 1 day), Day 15: (14 ± 2 days), Day 29: (28 ± 2 days), Day 43: (42 ± 3 days).

*Visits are indicated as calendar days, while the time post-dosing and the visit windows are indicated in the brackets.

If randomized to IV group (Arm 3), omit visits on Day 3 and Day 6.

Perform the following in-clinic or via telemedicine follow-up:

- Assessment of AEs and concomitant medications (in-clinic or telemedicine).
- Targeted physical exam, if clinically indicated. Based on the investigator's assessment of AEs/concomitant medication during telemedicine follow-up, an unscheduled visit (in-clinic) can be arranged to conduct a targeted physical exam. The investigator can also refer the subject to their healthcare provider or urgent care if more immediate medical attention is required.
- If WOCBP, confirm use of contraceptives.
- Provide counseling to participants on precautions/measures to prevent contracting SARS-CoV-2 infection.
- Only if participant becomes positive for SARS-CoV-2 at any time post-dosing during the study period: assess clinical status based on an Ordinal Outcome scale ([Appendix II](#)). Perform assessments via telemedicine if possible.

Anti-SARS-CoV-2 Immunoglobulin Intravenous (Human) (NP-028), abbreviated as COVID-HIG
EBS-CVH-006, Version 3.0, 18 Feb 2022

In-clinic staff or home healthcare attendant to perform the following:

- Serum sample for SARS-CoV-2 antibody PK assessment.
- Blood sample for safety laboratory assessments (chem 7 panel, total and direct bilirubin, ALT, AST, LDH, CBC) at Day 2 and Day 4 only. At other follow-ups, collect sample only if clinically indicated (as per investigator's discretion).
- Sample for urinalysis at Day 2 and Day 4 only. At other follow-ups, collect sample only if clinically indicated (as per investigator's discretion).
- Vital signs (resting ≥ 10 minutes) [body temperature, blood pressure (seated), pulse, SpO₂ (pulse oximetry) and respiratory rate] at Day 2 and Day 4 only. At other follow-ups perform only if clinically indicated (as per investigator/sub-investigator's assessment).

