9.4.3.5 Nasopharyngeal Swab Results

Nasopharyngeal swabs at Days 8, 15, 29, 43, and 57 will be analyzed for SARS-CoV-2 by RT-PCR and results will be reported by time point and administration route for the safety population.

In addition, the frequency and percentage of participants testing positive for COVID-19 will be reported for the safety population. The maximum COVID-19 symptom severity per participant using an Ordinal Outcome grading scale ([Appendix II](#)) will be tabulated for the SARS-CoV-2 positive population.

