APPENDIX II ORDINAL OUTCOME CATEGORIES AND CRITERIA

The following ordinal outcome categories will be used to classify the severity of illness in participants with laboratory-confirmed COVID-19.

Category	Clinical Severity	Criteria
1	Asymptomatic and no limitations in usual activity due to COVID-19	Both of the following criteria for symptoms and limitations: 
 • No symptoms related to COVID-19, either asymptomatic infection or resolution of prior symptoms, AND • Health status is at the same level as prior to SARS-CoV-2 infection and is without limitations due to COVID-19
2	Mild COVID-19 illness or minor limitations to usual activity	One of the following criteria indicating mild illness: 
 • Experiencing ≥ 1 symptoms of COVID-19 (see PIM) that were not present or are worse than pre-illness status; criteria for a higher category must not be met if involving a major symptom, such as difficulty breathing or confusion or any symptom of a 'severe' quality. • Minimal or mild interference in usual social or functional activity due to acute or resolving COVID-19 illness
3	Moderate COVID-19 illness and major limitations to usual activity	ALL of the following criteria for symptoms and limitations: 
 • One or more major symptoms including difficulty breathing, confusion, or any symptom of COVID-19 that is 'severe' in quality and also worse than pre-illness health status, AND • Without need for new oxygen supplementation (i.e., higher oxygen needs from pre-COVID levels for >24 hours), AND • Moderate or major limitations in usual social or functional activity due to acute or resolving COVID-19 illness 
NOTE: limitations must be the result of symptoms and not due solely to isolation precautions or quarantine

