#### 8.5 Exploratory Efficacy Endpoint

For subjects that become SARS-CoV-2 positive during the study period (at any time post-dosing on Day 1 and up to last follow-up visit/contact) an Ordinal Outcome Scale is collected to assess COVID-19 symptom severity. Maximum score on the Ordinal Outcome Scale is summarized by treatment arm and overall and presented in a subject listing for the SARS-CoV-2 Positive population with data available.

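### The maximum COVID-19 severity score is taken over point-in-time ratings with no recall period or rating interval, so an illness not rated while symptomatic is reported as Category 1

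*SAP*

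**What the plan says.** - **Endpoint.** Protocol 9.4.3.5 tabulates "The maximum COVID-19 symptom severity per participant using an Ordinal Outcome grading scale" for the SARS-CoV-2 Positive Population. SAP 8.5 implements this as follows: "Maximum score on the Ordinal Outcome Scale is summarized by treatment arm and overall".
- **What is rated.** At scheduled visits, Protocol 6.6 tells staff to "assess clinical status based on an Ordinal Outcome scale", under the condition "Only if participant becomes positive for SARS-CoV-2 at any time post-dosing during the study period". Sections 6.7 to 6.9 carry the same item for unscheduled, Day 57 and withdrawal visits.
- **Category 1.** Appendix II includes "No symptoms related to COVID-19, either asymptomatic infection or resolution of prior symptoms", together with a return to pre-infection health without limitations.
- **When rating stops.** Protocol 3.1 and the Synopsis have positive participants rated until symptoms resolve. SAP 2.2 gives only the last follow-up visit as the end. Neither document gives a rating interval or a recall period, and the scale has no row in either Schedule of Events.
- **Contacts.** Visits fall 1, 2, 3, 5, 7, 14, 28, 42 and 56 days after dosing (the IV arm omits days 2 and 5). Routine post-dose swabs are on Days 8, 15, 29, 43 and 57, with others if clinically indicated (Protocol 7.1.3). Unscheduled visits are at the investigator's discretion and may include a swab and the scale (Protocol 6.7).
- **Length of illness.** Protocol 1.5.2 says of mild disease that "symptomatic COVID-19 often resolves five to seven days (and up to 14 days) after symptom onset".

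**The concern.** A maximum over snapshots equals the worst point of the episode only if a snapshot was taken near that point. Here this can fail in two ways. The participant may first be found positive at a routine swab after recovery, so the first rating is already Category 1. Or the participant may be known positive while ill but have no rating before recovery, because no interval is set and the SAP no longer mentions rating until resolution.

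In both cases the later rating is correct for that day, and the derived maximum is wrong for the episode. An accurate current-status rating cannot exceed the episode's peak, so the error can only make illness look milder. This is the only endpoint listed for the exploratory objective. With few cases expected among 23 participants, one or two such records could change the table.

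**Working it through.** The documents give no figure for this endpoint, so there is nothing to reproduce. The check asks how often the visit schedule alone would miss an illness.

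**Inputs.** Visit days and windows come from Protocol 6.6 and 6.8. Illness of 5 to 7 days, and up to 14, comes from Protocol 1.5.2; 10 days is an intermediate value. Assumptions not in the documents: onset is uniform in time, visits fall on their nominal days, and there is no unscheduled contact.

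**Gaps after Day 8.** Nominal gaps are 7, 14, 14 and 14 days. The visit windows allow 14-day gaps to reach:
- Day 15 to 29: (28+2) − (14−2) = 18 days
- Day 29 to 43: (42+3) − (28−2) = 19 days
- Day 43 to 57: (56+3) − (42−3) = 20 days

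**Chance that no scheduled contact falls within an illness of d days.** In a gap of g days this is max(0, 1 − d/g). Over the whole 56 days it is the uncovered time divided by 56, where each gap contributes max(0, g − d).

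| d (days) | 14-day gap | Days 0 to 56 |
|---|---|---|
| 5 | 1 − 5/14 = 64% | (2 + 3×9)/56 = 29/56 = 52% |
| 7 | 1 − 7/14 = 50% | (3×7)/56 = 21/56 = 38% |
| 10 | 1 − 10/14 = 29% | (3×4)/56 = 12/56 = 21% |
| 14 | 0% | 0% |

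The two visits omitted in the IV arm do not change these values, because the gaps they leave are shorter than 5 days. A single gap stretched to 20 days would give 75%, 65%, 50% and 30% for 5, 7, 10 and 14 days.

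**Effect of unscheduled ratings.** If a share u of episodes is also rated off schedule while symptomatic, the 14-day-gap figure becomes (1 − d/14)(1 − u). For 5 and 7 days this is 32% and 25% at u = 50%, and 6% and 5% at u = 90%. The documents do not give u.

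**A case that follows both documents.** The Day 15 swab is negative. Symptoms run from Day 17 to Day 24 with no unscheduled visit. The Day 29 swab is still positive. All ratings on Days 29, 43 and 57 are Category 1, so the maximum is Category 1. The instruction to rate until symptoms resolve has not been broken, because positivity was unknown until after recovery.

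**The case against.** The strongest reply is that the protocol already requires rating until symptoms resolve and allows unscheduled visits with a swab and the scale. Someone known positive on Day 19 and ill until Day 24 should not wait until Day 29 for a first rating; that would be a failure to follow Protocol 3.1. This stands for cases identified while ill. It does not help cases found after recovery, it sets no interval, and SAP 2.2 leaves it out.

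Two stronger readings are tempting. A reader might infer that 64%, 50% or 29% of symptomatic cases would be scored as asymptomatic. The documents do not support that. The figures are chances of no scheduled contact during illness. A case with no off-schedule test enters the population only if a later swab is still positive; otherwise it is absent from the table, not scored Category 1. Neither persistence of positivity nor u is given.

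A reader might also subtract, say, two days for a test result, which gives 1 − 3/14 = 79%, 1 − 5/14 = 64% and 1 − 8/14 = 43%. But a positive result obtained between scheduled visits implies an off-schedule test, and this calculation gives no credit for a rating made around it.

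Other parts of the reply also stand. Five to seven days is only what often happens in mild illness. Mild limitation from resolving illness is Category 2, so the ratable period can outlast symptoms. COVID-19 is also tabulated as an AE and SAE (SAP 9.2.4), so severe illness would not be hidden. All arms receive the same product, and there is no untreated comparator.

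**Conclusion.** The point holds in a limited form. Taking the maximum of current-status ratings can understate the worst severity of an episode and, with accurate ratings, cannot overstate it. The size is bounded, not estimated. For illness starting after Day 15, the schedule alone misses 64%, 50% or 29% of 5-, 7- or 10-day episodes and none of 14 days. These are upper bounds on the problem at nominal spacing, given uniform onset and assuming that a participant seen while symptomatic is rated before recovery. Unscheduled ratings and cases that never test positive both lower the share that ends in a wrong Category 1. It is not established that many cases are affected. The endpoint is exploratory and descriptive, and no safety or PK conclusion depends on it. The change is still worth making, because a better measure is available at little cost.

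**What to change.** At each contact after a positive test, record current status and also the worst Appendix II category since the last contact (since symptom onset at the first such contact). In SAP 8.5, define the maximum over the worst-category values. In SAP 2.2, restore the protocol's rule that rating continues until symptoms resolve. The cost is one extra question at contacts already planned. The drawback is recall error over about 14 days, or up to 20 with the visit windows.

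Collection may be complete: the SAP is written largely in the past tense and was approved on 11 May 2022. In that case, list for each case the number of ratings and their timing relative to symptom onset and positive test. Report participants known to have had symptoms but with no rating during them as *not rated while symptomatic*, not as maximum Category 1. This needs no new data.

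Do not derive ordinal categories from AE grades. Under Protocol 8.1.1 a diagnosis replaces its signs and symptoms as the AE term, so the symptoms may not be recorded, and neither document maps AE grades to Appendix II.

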### 9 SAFETY ANALYSIS

All safety data are presented in the form of tabulations and listings, based on the Safety population.

#### 9.1 Extent of Exposure

The frequencies and percentages of subjects treated and completing study medication treatment are summarized in the disposition Section [7.1](#).

Extent of exposure is summarized overall and by baseline seronegative or seropositive SARS-CoV-2 antibody stratum and treatment arm for the Safety population. Route of administration (actual and not randomized), volume administered (mL), potency (AU), and total protein (g) are tabulated.

A subject listing of treatment exposure is provided.

Anti-SARS-CoV-2 Immunoglobulin Intravenous (Human) (NP-028), abbreviated as COVID-HIG  
EBS-CVH-006 Statistical Analysis Plan

## 9.2 Adverse Events

AEs are coded to system organ class (SOC) and preferred term (PT) according to the Medical Dictionary for Regulatory Activities (MedDRA). Treatment-emergent AEs, related AEs, SAEs, and AEs causing death or treatment/ study discontinuation are defined in Section 6.3. Only treatment-emergent AEs are included in the summary tables described below and “AE” refers to treatment-emergent AE, unless otherwise specified. AE severity is assessed on the scale of Grade 1 (mild) to Grade 4 (potentially life-threatening) as described in Section 5.8. Subjects having the same AE more than once are counted once for each PT and once within each SOC at the maximum severity or closest relationship.

A subject data listing of all AEs sorted by treatment arm, subject ID, and AE start date/time is provided for the Safety population with a “non-treatment-emergent” flag.

### 9.2.1 Overall Summary of Adverse Events

An overall summary of AEs is provided by SOC, PT, and treatment arm for the Safety population. The events are sorted in descending frequency of subjects in the ‘Total’ column for SOC, then PT, unless otherwise specified. Each of the line items below on the AE summary is a separate tabulation as well.

- Any AE
- Related AEs
- AEs occurring within 72 hours post-dosing
- Related AEs occurring within 72 hours post-dosing
- Grade 3 or higher AEs
- Grade 3 or higher related AEs
- MAAEs
- Related MAAEs
- SAEs
- Related SAEs
- COVID-19 AE and COVID-19 SAE
- AEs leading to death
- AEs leading to discontinuation of study treatment
- AEs leading to study withdrawal

### 9.2.2 Adverse Events of Special Interest

There were no AEs of special interest in this study.

Anti-SARS-CoV-2 Immunoglobulin Intravenous (Human) (NP-028), abbreviated as COVID-HIG  
EBS-CVH-006 Statistical Analysis Plan

### **9.2.3 Medically Attended Adverse Events**

MAAEs are tabulated using the MedDRA coded terms of SOC, PT, and treatment arm for all MAAEs and related MAAEs.

### **9.2.4 COVID-19**

Cases of COVID-19 as an AE and as an SAE are summarized separately by SOC, PT, and study arm.

## **9.3 Deaths, Other Serious Adverse Events, and Other Significant Adverse Events**

### **9.3.1 Deaths**

Deaths are not expected in this study with healthy participants. A tabulation and subject data listing of deaths is provided as appropriate, including the primary cause of death.

### **9.3.2 Serious Adverse Events**

SAEs are tabulated using the MedDRA coded terms of SOC, PT, and treatment arm for all SAEs and related SAEs. A subject data listing of SAEs is provided.

### **9.3.3 Adverse Events Leading to Discontinuation of Study Treatment and/or Study Withdrawal**

Separate tabulations are displayed for AEs leading to discontinuation of study treatment and withdrawal from the study by SOC, PT, and treatment arm.

## **9.4 Clinical Laboratory Tests**

### **9.4.1 Safety Laboratory Tests**

Clinical laboratory analytes included Na+, K+, Cl-, HCO3-, BUN, creatinine, glucose, total and direct bilirubin, ALT, AST, LDH, and CBC with differential. Urinalysis parameters included appearance, bilirubin, color, glucose, ketones, leukocyte esterase, nitrite, occult blood, pH, protein, specific gravity, and urobilogen. Clinical laboratory tests were required at Day 2 and 4; at other visits, tests were done as clinically indicated only. Clinical laboratory test results were assigned a toxicity grade by the investigator as described in Section 5.8.

Safety laboratory measurements are summarized as follows for the Safety population:

- Observed values and changes from baseline of continuous laboratory variables (hematology and serum chemistry) are summarized using descriptive statistics by study visit and treatment arm.
- Shifts from baseline in hematology and serum chemistry analyte values according to normal reference ranges (reported as 'Low,' 'Normal,' and 'High') or toxicity grades (Grade 0, 1-4) are summarized (number and percentages) by study visit and treatment arm.

Anti-SARS-CoV-2 Immunoglobulin Intravenous (Human) (NP-028), abbreviated as COVID-HIG  
EBS-CVH-006 Statistical Analysis Plan

- Frequency and percentage of subjects with the highest toxicity grade of abnormal hematology and serum chemistry laboratory values at any time on study are summarized by study visit and treatment arm. In this analysis, analytes with toxicity criteria for both increases and decreases are presented separately for each direction (e.g., sodium increased and sodium decreased).
- Urinalysis data are listed only.

All laboratory records (including local laboratory measurements if applicable) are provided in the subject data listings, with applicable toxicity grades or abnormal flags displayed.

#### **9.4.2 Pregnancy Testing**

Subject listings of FSH and pregnancy test results (serum and urine) are provided.

#### **9.4.3 Urine Drug Testing, Viral Serology Testing, and COVID-19 Testing at Screening or Baseline**

Urine drug screening, alcohol breath test, and viral serology testing results are provided in the subject listings. COVID-19 testing results at screening and baseline are also provided for those tests that occur only at screening and/or baseline.

